12. Patients who have an asthma exacerbation requiring systemic corticosteroids, hospitalization or emergency room visit during the screening or placebo run-in periods. Patients who experience an asthma exacerbation during screening may be re-screened 4 weeks after complete recovery from the exacerbation.
13. Patients who have had a respiratory tract infection or asthma worsening within 4 weeks of Visit 1. Patients who experience a respiratory tract infection or asthma worsening during screening may be re-screened after 4 weeks after recovery.
14. Patients with any chronic condition of the respiratory tract which in the opinion of the investigator may interfere with study evaluation or optimal participation in the study.
15. Patients with a history of chronic lung disease other than asthma, including (but not limited to) chronic obstructive pulmonary disease (as defined by Global Initiative For Chronic Obstructive Lung Disease (GOLD) standards), bronchiectasis, (non-clinically significant bronchiectasis may be allowed provided recent (within 3 months prior to Visit 101) computed tomography (CT) scan proof is available), sarcoidosis interstitial lung disease, cystic fibrosis, and tuberculosis.
16. Patients with a history of conditions other than asthma or allergic rhinitis that could result in elevated eosinophils (e.g., hypereosinophilic syndromes, Churg-Strauss Syndrome,

- eosinophilic esophagitis). Patients with known parasitic infestation within 6 months prior to Visit 1 are also excluded.
17. Patients with uncontrolled diabetes having an hemoglobin A1c (HbA1c) test result  $\geq 8\%$  at the Visit 1 laboratory test.
  18. Patients who have a clinically significant laboratory abnormality at the Visit 1 laboratory test including (but not limited to):
    - Total white blood cell count  $< 2500$  cells/ $\mu\text{L}$ ;
    - Aspartate aminotransferase (AST) or alanine aminotransferase (ALT)  $> 2.0$  X ULN or total bilirubin  $> 1.3$  X ULN;
    - Estimated Glomerular Filtration Rate (eGFR) by the modification of diet in renal disease study (MDRD) equation or Bedside Schwartz equation  $< 55$  mL/minute/ $1.73$  m^2.

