#### **9.5.2.4 Laboratory data**

All laboratory data will be listed with abnormal values flagged. The laboratory values and the change from baseline for continuous laboratory parameters will be summarized at each visit. A frequency table of results for categorical laboratory parameters will be produced for the whole study duration.

Shift tables relative to the normal reference ranges will be used to summarize the change from baseline to post-baseline for each laboratory parameter. For each laboratory parameter, the patients will be classified into one of the four mutually exclusive groups (low, normal, high, and low + high).

For selected laboratory parameters, the number and percentage of patients with newly occurring or worsening laboratory abnormalities meeting the clinically notable criteria will be summarized by laboratory parameter at any time-point over the treatment period, considering all post-baseline data from scheduled, unscheduled and premature discontinuation visits. Patients with any newly occurring or worsening value meeting the clinically notable criteria will be counted under the applicable criteria.

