2.1.1.1 Baseline definition

Data from unplanned visits prior to screening are not included in analysis. In general, baseline is defined as the last assessment taken prior to the first dose of study drug at Day 1 (Visit 201).

Checks will be performed to ensure the assessments were taken prior to the first dose of study drug on Day 1 (Visit 201). If the assessment is missing or not confirmed to be pre-dose, then the last available non-missing assessment will be used as baseline. Missing baseline pre-dose FEV1, daytime asthma symptoms, total daily SABA use and AQLQ+12 will be assumed to be missing at random as assessments are performed prior to any knowledge of treatment allocation and will be imputed using the mean value of all randomized patients.

Table 2-1 Baseline definition of analysis parameters

Parameter	Baseline assessment	Detail
ACQ-5, AQLQ [REDACTED]	Last assessment prior to the first dose of study drug on Day 1	If the Day 1 assessment is missing the last available assessment (scheduled or unscheduled) taken prior to the first dose of study drug will be used.

Lung function (FEV ₁)	Average of the two FEV ₁ assessments taken at 45 minutes and 15 minutes prior to the first dose of study drug on Day 1	Checks will be performed to ensure both values were taken prior to the first dose of study drug. If one of the 45 and 15 min values is missing (or is not confirmed to be pre-dose) then the remaining non-missing value will be taken as the baseline. If both assessments are missing (or are not confirmed to be pre-dose) then the last available FEV ₁ measurement (scheduled or unscheduled) prior to Day 1 will be used for baseline.
eDiary data (Daytime asthma symptoms)	Average of the mean daytime asthma symptom score from Visit 101 to Day 1	The baseline score will be calculated as long as there are at least 4 days with non-missing eDiary data. Noted that the morning assessment for Day 1 counts towards the baseline.
eDiary data (Total daily use of SABA)	Average of total daily SABA use from Visit 101 to Day 1	The baseline score will be calculated as long as at least 4 days with non-missing eDiary data. Noted that the morning assessment for Day 1 counts towards the baseline while the evening assessment for Day 1 counts as the treatment period.

Laboratory data (hematology, clinical chemistry, urine analysis)	Last available assessment (scheduled or unscheduled) prior to dosing on Day 1	

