2.7.3.3 Notable values

For selected laboratory parameters, abnormalities occurring at any time-point over the treatment period, considering all post-baseline data from scheduled, unscheduled and premature discontinuation visits will be summarized. Patients with any newly occurring or worsening on-treatment value meeting the clinically notable criteria will be counted under the applicable criteria.

For a patient to meet the criterion of a newly occurring clinically notable value, the patient needs to have a baseline value which is not clinically notable for that parameter. For a patient to meet the criterion of a worsening clinically notable value, the patient needs to have a baseline value which is not clinically notable and have a worse post-baseline value. For patients with a missing baseline value, any post-baseline notable value will be considered as newly occurring.

The criteria for clinically notable values are presented in [Table 6-4-2](#).

Laboratory test units will be converted to standard units. Based on agreement within our standards, if we have a multi-region study the Blood Urea Nitrogen (BUN) / Urea test would be represented as BUN [mg/dL] for the regions used to conventional results (US, Latin America) and as Urea [mmol/L] for the regions used to SI (the international system of units) results. Therefore, both BUN and Urea parameters will be included in the data.

BUN is always reported as mg/dL and Urea as mmol/L. BUN and Urea are the same measurement in the lab and should be considered the same test. Hence, for the summary tables, it is expressed in SI units. Conversion to SI units includes the factor that incorporates a conversion from BUN to Urea as well as a conversion from mg/dL to mmol/L. This is necessary because BUN is Urea Nitrogen, not Urea and there are two nitrogens in each urea molecule. The factor of 0.357 converts BUN in mg/dL to Urea in mmol/L.

Listings of patients with notable laboratory values will be provided by laboratory parameter, treatment group, and patient number.

Liver function tests

To evaluate potential drug-induced liver injury, newly occurring or worsening abnormalities in liver function tests will be evaluated (see [Table 6-4-3](#) for a summary of the notable values).

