When a criterion contains multiple laboratory parameters, the criterion will only be considered to be met when all conditions occur at the same time (i.e., in the same sample). A case where all criteria are met at a post-baseline time point but not met at baseline will be considered as newly occurring. A case will be considered as worsening if all the criteria are met at baseline and at least one component is worsening from baseline, irrespective of whether the other(s) are better.

The number and percentage of patients with newly occurring liver enzyme abnormalities any time post-baseline will be summarized. Listings of patients with notable liver function test lab values and liver events will be provided.

To evaluate drug induced serious hepatotoxicity eDish plots will be presented. The eDish plot will reflect the worst value of each of the parameters; they do not need to occur at the same visit.

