6.4 Laboratory parameters derivations

The following table shows the criteria for clinically notable laboratory values. Not all parameters have notable criteria defined.

Table 6-4-1 Direction of interest for worst case value for laboratory parameters

Laboratory Parameter	Direction of interest for worst case value
A. Hematology	
Basophils	High
Eosinophils	High
Hematocrit	Low
Hemoglobin	Low
Lymphocytes	Low and high
Monocytes	High
Neutrophils	Low and high
Platelets	Low and high
RBC	Low
WBC total	Low and high
B. Chemistry	
Albumin	Low
Sodium	Low and High
Alkaline Phosphatase	High
ALT/SGPT	High
AST/SGOT	High
Bilirubin Total	High
Blood Urea Nitrogen (BUN)	High
CPK	High
Creatinine	High
Gamma GT	High
Glucose	Low and high
Potassium	Low and high
Uric acid	High

Table 6-4-2 Clinical notable criteria for selected laboratory tests

Laboratory parameter (unit)	Bound for notably low values	Bound for notably high values
Hematology		
Hematocrit (v/v)		
Male aged 12-17	0.34	
Male aged 18-65	0.37	
Male aged >=66	0.34	
Female aged 12-65	0.32	
Female aged >=66	0.31	

Laboratory parameter (unit)	Bound for notably low values	Bound for notably high values
Hemoglobin (g/L)		
Male aged 12-17	100	
Male aged >=18	110	
Female	95	
Thrombocytes (x10E ⁹ /L)	75	700
WBC's (x10 ⁹ /L)	2.8	16.0
Chemistry		
Alkaline Phosphatase (IU/L)	-	3xULN
Total Bilirubin (µmol/L)	-	34.2
Creatinine (µmol/L)		176.8
Potassium (mmol/L)	3	6
Glucose (mmol/L)	2.78	9.99
ALT/SGPT (U/L)	-	3 x ULN
AST/SGOT (U/L)	-	3 x ULN
BUN/ Urea (mmol/L)		9.99
Sodium (mmol/L)	125	160
Gamma GT (U/L)		3 x ULN
CPK (IU/L)		4 x ULN
Urinalysis		
Dipstick blood		≥ 2+
Dipstick glucose		≥ 2+
Dipstick leukocytes		≥ 2+
Dipstick protein		≥ 2+

v = volume, ULN = upper limit of normal

Table 6-4-3 Notable liver function test values

Criterion
ALT > 3 x ULN ALT > 5 x ULN ALT > 8 x ULN ALT > 10 x ULN ALT > 20 x ULN
ALT or AST > 3 x ULN ALT or AST > 5 x ULN ALT or AST > 8 x ULN ALT or AST > 10 x ULN ALT or AST > 20 x ULN
Total Bilirubin > 1 x ULN Total Bilirubin > 1.5 x ULN Total Bilirubin > 2 x ULN Total Bilirubin > 3 x ULN
ALP > 1.5 x ULN ALP > 2 x ULN ALP > 3 x ULN ALP > 5 x ULN
ALT or AST > 3 x ULN and Total Bilirubin > 1.5 x ULN ALT or AST > 3 x ULN and Total Bilirubin > 2 x ULN ALT or AST > 5 x ULN and Total Bilirubin > 2 x ULN ALT or AST > 8 x ULN and Total Bilirubin > 2 x ULN ALT or AST > 10 x ULN and Total Bilirubin > 2 x ULN ALT or AST > 20 x ULN and Total Bilirubin > 2 x ULN

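### SAP 2.7.3.3 defines a worsening notable laboratory value from a non-notable baseline, so a patient already notable at baseline who deteriorates is not counted

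*SAP*

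**What the plan says.** Protocol 9.5.2.4 commits to a by-parameter table in which the "number and percentage of patients with newly occurring or worsening laboratory abnormalities meeting the clinically notable criteria will be summarized by laboratory parameter". It does not define worsening.

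SAP 2.7.3.3 repeats that commitment for on-treatment values and then defines the two categories for single parameters:

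- Newly occurring: for a "newly occurring clinically notable value, the patient needs to have a baseline value which is not clinically notable for that parameter".
- Worsening: for a "worsening clinically notable value, the patient needs to have a baseline value which is not clinically notable and have a worse post-baseline value".

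A missing baseline is handled separately: any later notable value then counts as newly occurring.

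Under the liver function tests subheading of the same section, criteria that combine several parameters follow a different rule: "A case will be considered as worsening if all the criteria are met at baseline and at least one component is worsening from baseline". That subsection opens by saying that both new and worsening liver abnormalities will be evaluated, but its count sentence reads: "The number and percentage of patients with newly occurring liver enzyme abnormalities any time post-baseline will be summarized".

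**The concern.** Worsening should describe a patient who already has the abnormality and gets worse. Here it starts from a patient who does not have it. The category then duplicates newly occurring, and the patients it should capture drop out of the count. Laboratory tests are part of secondary objective 4, and for most parameters this table is the only by-arm number and percentage of notable values. SAP Section 4 also drops the normal-range shift tables promised in Protocol 9.5.2.4, so those cannot fill the gap. The readable part of SAP Section 4 lists no change to the meaning of worsening.

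**Working it through.** The plan gives no figure to reproduce, so the check is of the logic first and then of whether affected patients can exist.

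**1. The rule as written.** Let B be the baseline value and P the post-baseline value.

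- Newly occurring: B not notable (or missing), and P notable.
- Worsening as written: B not notable, P worse than B, and P notable.
- Counted: either of the above.

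If B is not notable and P is notable, the case is already newly occurring. Worsening as written is therefore a subset of newly occurring and adds nobody. If B is notable, both definitions fail at the first condition, however bad P is.

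**2. Examples against the bounds in SAP Table 6-4-2.**

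| Parameter (bound) | B to P | Counted as written | Counted if worsening requires B notable |
|---|---|---|---|
| WBC (low 2.8 x10^9/L) | 2.9 to 2.7 (-6.9%) | Yes | Yes |
| WBC | 2.6 to 1.5 (-42.3%) | No | Yes |
| CPK (high 4 x ULN) | 1 to 6 | Yes | Yes |
| CPK | 5 to 12 | No | Yes |
| CPK | 5 to 4.5 (improves) | No | No |
| Glucose (high 9.99 mmol/L) | 11 to 20 | No | Yes |

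Percentages: (2.7 - 2.9)/2.9 = -6.9%; (1.5 - 2.6)/2.6 = -42.3%.

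For CPK in steps of 0.1 x ULN up to 19.9, there are 159 notable baseline values (4.1 to 19.9), hence 159 x 158 / 2 = 12,561 pairs with a notable baseline and a worse later value. All 12,561 are missed as written and none after the correction. This shows the logic only; it does not estimate how many trial patients are affected.

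**3. Can a randomized patient be notable at baseline?** Yes, for three reasons.

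- Exclusion 18 in Protocol 4.2 names WBC below 2500 cells/uL, that is 2.5 x10^9/L, but the notable bound is 2.8. A patient between 2.5 and 2.8 passes the named limit and is already notable, unless the investigator judges the value clinically significant.
- Exclusion 18 covers "Patients who have a clinically significant laboratory abnormality at the Visit 1 laboratory test including (but not limited to") the limits it lists. SAP Table 2-1 defines laboratory baseline as "Last available assessment (scheduled or unscheduled) prior to dosing on Day 1". Protocol Table 6-1 schedules Visit 1 at Day -21 and re-samples blood and urine at Visit 201, about three weeks later. A baseline can thus be notable without having been screened.
- SAP Table 6-4-2 ("Clinical notable criteria for selected laboratory tests") has 4 hematology + 11 chemistry + 4 dipstick = 19 parameters. Six have a numeric Visit 1 limit: WBC, ALT, AST, bilirubin, creatinine (through eGFR) and CPK (statin users only). The other 19 - 6 = 13 have none of their own: hematocrit, hemoglobin, platelets, ALP, potassium, glucose (limited only indirectly, through HbA1c), urea, sodium, gamma GT and the four dipstick tests.

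**4. Size.** The documents give neither baseline frequencies nor worsening rates. Assumed: 0.5% to 3% notable at baseline for a given parameter, and 20% to 50% of those worsening, with 325 per arm (Protocol 9.8).

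- Low: 325 x 0.005 x 0.20 = 0.3 patients per arm (0.1%).
- High: 325 x 0.03 x 0.50 = 4.9 patients per arm (1.5%).

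**The case against.** The strongest reply is that this is a drafting slip with visible intent and limited reach. The protocol does not define worsening, the SAP repeats the protocol's commitment, and the liver rule shows what was meant. A slip would not appear in a list of planned changes, so its absence from SAP Section 4 proves little. All of that is fair, but it explains the error without making the sentence right. A program that follows the text gives the wrong count, and one that follows the intent contradicts the SAP.

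Other outputs soften the loss:

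- Patients left out still appear in the notable-value listings. For continuous parameters they also enter the worst-case and change-from-baseline summaries (SAP 2.7.3.1 and 2.7.3.2).
- Dipstick results have by-treatment frequency tables that include worst-case values, whatever the baseline.
- ALT, AST, bilirubin and ALP have graded thresholds in SAP Table 6-4-3, so crossing a higher tier can count as newly occurring there. Only deterioration within a tier is lost.
- Clinically significant abnormalities are adverse events under Protocol 7.1.
- Judgement-based exclusions (hypokalemia in criterion 19, hepatic disease in criterion 35) make some notable baselines less likely. The only scheduled post-baseline laboratory samples are at treatment discontinuation and Visit 299.

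These points stand and keep the impact small. They do not supply the promised count for parameters such as WBC, platelets, glucose, potassium, sodium, urea, gamma GT and CPK, which have no further tier.

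One further point stands. Five parameters have both a low and a high bound (platelets, WBC, potassium, glucose, sodium). Deleting *not* leaves the direction of worse unstated for them.

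**Conclusion.** The concern holds. The single-parameter worsening rule in SAP 2.7.3.3 is wrong as written: it adds no patient and omits every patient who is notable at baseline and deteriorates. It conflicts with the liver rule in the same section and does not deliver the count promised in Protocol 9.5.2.4. Separately, the liver count sentence leaves out the worsening cases that the subsection says it will evaluate.

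The consequence is an incomplete descriptive safety count, with no bearing on efficacy, alpha or sample size. The number affected is probably small. The 0.3 to 4.9 patients per arm per parameter rests wholly on assumed frequencies and is not a figure from the documents. It should be corrected because the omitted patients are those whose existing abnormality worsened on treatment.

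**What to change.** 1. In SAP 2.7.3.3, delete *not* from the worsening sentence, so that worsening requires a clinically notable baseline and a worse post-baseline value.
2. In the liver function tests paragraph, extend the count sentence to cover newly occurring or worsening abnormalities, matching the aim stated at the start of that subsection.
3. For the five parameters with two bounds, say that new and worsening are judged separately against the low and the high bound.
4. Optionally, point to the corrected definition from SAP 2.7.4.1 (QTcF) and 2.7.4.2 (vital signs). Both use the same phrase without defining it. Their change-from-baseline criteria already cover much of the gap, so this is for clarity only.

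The cost is one deleted word, two added words and one or two clarifying sentences. No new data are needed. The programming change should be small if made before database lock, although the documents do not show the code.

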2.7.4 Other safety data

2.7.4.1 ECG data

ECG measurements include heart rate, QT interval, RR interval, PR interval, QRS duration, and Fridericia's QTc (calculated as $QTcF = QT / \sqrt[3]{RR}$ (in seconds), where $\sqrt[3]{}$ denotes the cube root). Furthermore, an overall interpretation of the central cardiologist will be provided as well as a specification of abnormal findings.

ECG data measured more than 7 days after last intake of study drug are regarded as post treatment data and will not be summarized. All data will be included in the analyses regardless of rescue medication use.

Summary of absolute values and change from baseline

Absolute values and change from baseline summarized by parameter, and visit.

Clinically notable values

- The number and percentage of patients with newly occurring or worsening clinical notable QTcF values (see Table 2-3) summarized by scheduled post-baseline visit and additionally at any time on treatment considering all post-baseline data from scheduled, unscheduled and premature discontinuation visits.

Table 2-3 Clinically notable criteria for QTcF (Fridericia's formula)

ECG parameter (unit)	Clinically notable range
Value considering newly occurring or worsening cases	
QTc (msec)	≥ 450 (male)
QTc (msec)	≥ 460 (female)
QTc (msec)	> 500 (both)
Change from baseline	
QTc	1 - < 30
QTc	30 – 60
QTc	> 60

Clinically relevant values

- A summary table will also be produced for number and percentage of subjects with clinically relevant QT and QTcF intervals (irrespective of the time point) using the following categories:
 - any treatment emergent (new) QTcF ≥ 450 ms – 480 ms, > 480 ms – 500 ms or > 500 ms
 - QTcF increase from baseline of 30 ms – 60 ms, > 60 ms
 - QTcF increase from baseline of ≥ 30 ms plus QTcF interval ≥ 450 ms, > 480 ms or > 500 ms

- d. QTcF increase from baseline of ≥ 60 ms plus QTcF interval ≥ 450 ms, > 480 ms or > 500 ms
- The number and percentage of subjects with noteworthy PR, QRS and HR interval changes will be reported using the below categories:
 - a. New PR > 200 ms to ≤ 220 ms; and > 220 ms
 - b. New QRS > 110 ms to ≤ 120 ms; and > 120 ms
 - c. PR increase $> 25\%$ to a value > 200 ms
 - d. QRS increase $> 25\%$ to a value > 120 ms
 - e. HR decrease $> 25\%$ to a HR < 50 bpm
 - f. HR increase $> 25\%$ to a HR > 100 bpm

Overall ECG interpretation

- Summary of ECG abnormalities will be produced on following variables: The number and percentage of subjects with newly occurring or persistent/recurrent on-treatment ECG abnormalities in overall ECG interpretation at any time point
 - The number and percentage of subjects with newly occurring or persistent/recurrent on-treatment ECG abnormalities by evaluation type and abnormality finding at any time point.

If patients had at least once ECG abnormality at baseline, the baseline flag will be abnormal. Similarly, for post baseline visits, if patients had at least once ECG abnormality at a visit, then ECG is abnormal at that visit else normal.

- Patients with notable post-baseline ECG values will be listed. Box plots of ECG by scheduled visit and treatment for the parameters: QTcF and summary (mean) heart rate will be presented.

2.7.4.2 Vital signs

Vital signs measurements include systolic and diastolic blood pressure (SBP and DBP), pulse rate, height and body weight. Vital signs data taken on or after the time of the first intake of study drug and until 7 days after the last intake of study drug are regarded as on-treatment data. Vital signs data measured more than 7 days after last intake of study drug are regarded as post-treatment data and will not be summarized. All data will be included in the analyses regardless of rescue medication use.

The following analyses will be performed by treatment group:

- absolute on-treatment values and change from baseline summarized by parameter, and visit
- the number and percentage of patients with newly occurring or worsening notable vital signs on-treatment values (see [Table 6-5-1](#) for definition of notable values) summarized by parameter (except height), at any time on treatment considering all post-baseline data from scheduled, unscheduled and premature discontinuation visits
- Vital signs will also be summarized by clinically relevant categories:
 1. Pulse rate: < 40 bpm, $40 - 90$ bpm, and > 90 bpm
 2. Systolic blood pressure: < 90 mm Hg, $90 - 140$ mm Hg, and > 140 mm Hg

3. Diastolic blood pressure: < 50 mm Hg, 50 – 90 mm Hg, and > 90 mm Hg.

Number and percentage of patients with clinically relevant on-treatment vital signs values that occur at any time post-baseline will be summarized for minimum and maximum post-baseline values.

